9.5.3 Biomarker Assessments

The following biomarker assessments will be done:

- *FGFR1* and 11q amplification status in tumor tissue assessed by FISH, CISH, NGS, and qPCR
- RNA expression of various genes related to signaling pathways inhibited by lucitanib including, but not limited to *FGFR1*, *FGF3/4/19*, and additional FGF family members
- Protein expression of *FGFR1* as determined by IHC

FFPE tumor tissue will be used for *FGFR1* and/or 11q amplification confirmatory central laboratory testing. Detailed sample handling instructions are provided in the Laboratory Manual. Tumor samples may be used to develop a tissue-based diagnostic test.

Following disease progression, patients will be encouraged to undergo an optional post-treatment tumor biopsy before subsequent-line therapy is initiated.

Sample handling instructions will be provided in a separate Laboratory Manual.

9.5.4 Population PK Assessments

Plasma levels of lucitanib will be measured on pre-dose samples collected on Day 15 of Cycle 1 and Day 1 of Cycles 2, 3, and 5. An additional sample will be collected on Cycle 2, Day 1, 1–3 hours post-dose. Sparse blood sampling for POPPK analyses will be conducted in all patients treated with lucitanib. Refer to the Laboratory Manual for sample handling instructions.

9.5.5 PK Sub Study

Up to 20 patients will participate in the PK sub study. PK sampling will be performed at specified time points on each on the following two days:

- Day –7: lucitanib in tablet formulation
- Day 1: lucitanib in capsule formulation

The dose assigned for patients participating in the PK sub study will be the same for Days -7 and 1 and depends on the version of the amendment approved at the time of patient enrollment (Amendment #3: 15 mg; Amendment #4: 10 mg).

The total time from the Day -7 visit to the Cycle 1 Day 1 visit must not be fewer than 7 days, but may be greater than 7 days, if necessary. Lucitanib will not be taken between Day -7 and Cycle 1, Day 1.

PK specimens will be taken on Day -7 and Day 1 PK specimens will be collected 5–10 min pre-dose, and post-dose at 15 (± 2) min, 30 (± 3) min, 1 hr (± 5 min), 1.5 hr (± 5 min), 2.5 hr (± 10 min), 4 hr (± 15 min), 6 hr (± 15 min), 8 hr (± 15 min), 10 hr (± 30 min) (optional), and 24 hr (± 30 min). Refer to the Laboratory Manual for sample handling instructions.

9.5.6 Pharmacogenomic Assessment

Blood draw for pharmacogenomic assessment will be drawn either during Screening or on C1D1 prior to dosing.

9.5.7 Pharmacodynamic Evaluations

For all patients PD evaluations will be performed at screening, pre-dose on Day 1 of each treatment cycle, on Day 15 of Cycle 1, and at the End-of-Study visit for analysis of ctDNA and measurement of circulating plasma levels of, including but not limited to, FGF-2, FGF-23, sVEGFR1, VEGF-A, sCSF-1R, and CSF-1.

Blood samples collected for ctDNA analysis will be processed locally to yield plasma (ctDNA fraction) and buffy coats (genomic DNA fraction). Genomic DNA extracted from the buffy coat or whole blood may be compared to tumor DNA so that molecular alterations unique to the tumor that may modulate response or resistance to study-assigned therapy can be unambiguously identified.

Analysis may be performed on a subset of patients if it becomes clear that the analysis will have limited scientific value in some patients (e.g., because of a very low titer of ctDNA), or if there are not enough serially collected samples from individual patients to allow for adequate biomarker evaluation.

Samples may be used for the development of a blood-based diagnostic test.

Please refer to the Laboratory Manual for details on collecting and processing of PD blood samples.

9.5.8 Quality-of-Life Assessments

QoL will be measured using the FACT-B questionnaire ([Appendix D](#)), which will be administered on Day 1 of Cycles 1, 3, 5, and 7. After Cycle 7, questionnaires will be collected every 3 cycles (on Day 1 Cycles 10, 13, 16, etc.), and at End-of-Study.

9.5.9 Patient Diary

Patient diaries will be provided to patients and should be brought to the site at each visit for review. Patient will use the diary to note the date and dose of lucitanib administration. BP measurements (see [Section 9.5.1.3](#)) will also be recorded in the diary.

10 ADVERSE EVENT MANAGEMENT

10.1 Definition of an Adverse Event

An AE is defined as any untoward medical occurrence in a patient administered a medicinal product that does not necessarily have a causal relationship with this treatment. An AE can, therefore, be any unfavorable and unintended sign (including an abnormal laboratory finding), symptom, or disease temporally associated with the use of an investigational product, whether or not related to the investigational medicinal product. This includes an exacerbation of pre-existing conditions or events, intercurrent illnesses, drug interaction, or the significant worsening of the indication under investigation that is not recorded elsewhere in the eCRF under specific efficacy assessments. Anticipated fluctuations of pre-existing conditions, including the disease under study, that do not represent a clinically significant exacerbation or worsening are not considered AEs.

It is the responsibility of the investigator to document all AEs that occur during the study. AEs should be elicited by asking the patient a nonleading question (e.g., “Have you experienced any new or changed symptoms since we last asked/since your last visit?”). AEs will be reported on the AE eCRF. Symptoms reported spontaneously by the patient during the physical examination will also be documented on the AE eCRF (not on the physical examination eCRF, which is reserved for physical signs or findings).

10.2 Definition of a Serious Adverse Event

An SAE is any untoward medical occurrence that occurs at any dose that:

- Results in death. Death may occur as a result of the underlying disease process. Nevertheless, any event resulting in death during the reporting period must be treated as an SAE and reported as such. All deaths occurring within 28 days of the last administration of lucitanib should be reported as SAEs
- Is life-threatening (patient is at immediate risk of death from the event as it occurred)
- Requires in-patient hospitalization (formal admission to a hospital for medical reasons) or prolongation of existing hospitalization
- Results in persistent or significant disability/incapacity
- Results in a congenital anomaly/birth defect

Important medical events that may not result in death, are not life-threatening, or do not require hospitalization may be considered SAEs when, based on appropriate medical judgment, they may jeopardize the patient and may require medical or surgical intervention to prevent one of the outcomes listed in this definition. Examples of such events include allergic bronchospasm requiring intensive treatment in an emergency room or at home, blood dyscrasias, PRES, or seizures that do not result in in-patient hospitalization, or the development of drug dependency or drug abuse.

10.3 Events or Outcomes Not Qualifying as Serious Adverse Events

The following are not considered SAEs and do not need to be reported to the sponsor:

- Pre-planned or elective hospitalization including social and/or convenience situations (e.g., respite care)
- Overdose of either Clovis study drug or concomitant medication unless the event meets SAE criteria (e.g., hospitalization). However, the event should still be captured as a non-serious AE on the appropriate eCRF page
- Events of progression of the patient's underlying cancer as well as events clearly related to progression of the patient's cancer (signs and symptoms of progression) should not be reported as an SAE unless the outcome is fatal during the study or within the safety reporting period. If the event has a fatal outcome during the study or within the safety reporting period, then the event of Progression of Disease must be recorded as an AE and as a SAE with CTCAE Grade 5 (fatal outcome) indicated
- Diagnosis of progression of disease or hospitalization due to signs and symptoms of disease; progression alone should not be reported as SAEs

10.4 Clinical Laboratory Assessments as Adverse Events and Serious Adverse Events

It is the responsibility of the investigator to assess the clinical significance of all abnormal values as defined by the list of reference ranges from the local laboratory. In some cases, significant changes in laboratory values within the normal range will require similar judgment.

An abnormal laboratory value that is not already associated with an AE is to be recorded as an AE only if any one of the following criteria is met:

- An action on the study drug is made as a result of the abnormality
- Intervention for management of the abnormality is required
- At the discretion of the investigator should the abnormality be deemed clinically significant

10.5 Pregnancy or Drug Exposure during Pregnancy

If a patient becomes pregnant during the study the investigator is to stop dosing with lucitanib immediately.

A pregnancy is not considered to be an AE or SAE; however, it must be reported to the sponsor using the Pregnancy Report Form within the same timelines as an SAE ([Section 10.8](#)). **This applies to female patients as well as female partners of male patients.**

A pregnancy should be followed through to outcome, whenever possible. Once the outcome of the pregnancy is known, the Pregnancy Outcome Report Form should be completed and reported to the sponsor.

AEs or SAEs that occur during pregnancy will be assessed and processed according to the AE or SAE processes using the appropriate AE or SAE forms.

10.6 Recording of Adverse Events and Serious Adverse Events

AEs will be assessed from the time of first dose of lucitanib through 28 days after the last protocol-specified treatment administration. Study-procedure-related events that occur after signing of the ICF and before administration of lucitanib will also be collected as AEs.

In order to avoid vague, ambiguous, or colloquial expressions, the AE should be recorded in standard medical terminology rather than the patient's own words. Whenever possible, the investigator should combine signs and symptoms that constitute a single disease entity or syndrome. For example, fever, shortness of breath, and cough may be reported as pneumonia, if that is a suspected or final diagnosis.

The existence of an AE may be concluded from a spontaneous report of the patient; from the physical examination; or from special tests such as the ECG, laboratory assessments, or other study-specified procedure (source of AE).

Each AE is to be evaluated for duration, severity, seriousness, and causal relationship to the investigational drug. The action taken and the outcome must also be recorded.

SAEs that occur during the study or within 28 days after receiving the last dose of protocol-specified treatment, whether or not related to study drug, must be reported to the sponsor/designee within 24 hours of knowledge of the event ([Section 10.8](#)). After the 28-day specified window, only SAEs considered to be treatment-related should be reported.

10.6.1 Intensity of Adverse Events

The severity of the AE will be graded according to the NCI CTCAE Version 4.03 grading scale. For AEs not covered by NCI CTCAE Version 4.03, the severity will be characterized as mild, moderate, severe, or life-threatening according to the following definitions:

- Mild events are usually transient and do not interfere with the patient's daily activities
- Moderate events introduce a low level of inconvenience or concern to the patient and may interfere with daily activities
- Severe events interrupt the patient's usual daily activities and hospitalization (or prolongation of hospitalization) may be required
- Life-threatening events require urgent intervention to prevent death

10.6.2 Causal Relationship of Adverse Events to Investigational Medicinal Products

Medical judgment should be used to determine the cause of the AE considering all relevant factors such as, but not limited to, the underlying study indication, coexisting disease, concomitant medication, relevant history, pattern of the AE, temporal relationship to the study medication, and dechallenge or rechallenge.

Not Related

- An AE that is clearly due to extraneous causes (e.g., concurrent disease, concomitant medications, disease under study, etc.)
- It does not follow a reasonable temporal sequence from administration of study drug
- It does not follow a known pattern of response to study drug
- It does not reappear or worsen when study drug is restarted
- An alternative explanation is likely but not clearly identifiable

Related

- An AE that is difficult to assign to alternative causes
- It follows a strong or reasonable temporal sequence from administration of study drug
- It could not be reasonably explained by the patient's clinical state, concurrent disease, or other concomitant therapy administered to the patient
- It follows a known response pattern to study drug
- It is confirmed with a positive rechallenge or supporting laboratory data

10.6.3 Outcome and Action Taken

The investigator will record the action taken and outcome for each AE according to the following criteria:

Action Taken with Study Drug

- None
- Dose reduced/delayed
- Lucitanib temporarily interrupted
- Lucitanib permanently discontinued
- Other (specify)

Outcome

- Recovered
- Recovered with sequelae
- Improved
- Ongoing
- Death

- Lost to follow-up

10.7 Follow-Up of Adverse Events and Serious Adverse Events

All AEs occurring during the study are to be followed up in accordance with good medical practice until resolved; judged no longer clinically significant; or, if a chronic condition, until fully characterized through 28 days after the last dose of protocol-specified treatment. Any SAEs must be followed until resolution or stabilization.

10.8 Regulatory Aspects of Serious Adverse Event Reporting

All SAEs, regardless of relationship to study drug, must be reported to the sponsor/designated safety contact within 24 hours of knowledge of the event, according to the procedures below. It is important that the investigator provides an assessment of the relationship of the SAE to study treatment at the time of the initial report. The Clinical Trial Serious Adverse Event Report Form must be used for reporting SAEs.

While not considered an SAE, pregnancy occurring in a female patient or in the female partner of a male patient must also be reported to the sponsor/designated safety contact as soon as the event is known by the clinical site. If the pregnancy occurs in a female patient, study drug should be stopped immediately. Notification to the sponsor/designee should take place via facsimile or email utilizing the Pregnancy Report Form.

Further details on SAE/pregnancy reporting can be found in the investigator's file.

Clovis or its designee is responsible for submitting reports of AEs associated with the use of the drug that are both serious and unexpected to the U.S. Food and Drug Administration (FDA), according to 21 Code of Federal Regulations (CFR) 312.32 and to the European regulatory authorities according to the European Commission Clinical Trials Directive (2001/20/EC); and to other regulatory authorities, according to national law and/or local regulations, as applicable. All investigators participating in ongoing clinical studies with the study medication will receive copies of these reports for prompt submission to their IRB or IEC.

Clovis or its designee will submit all safety updates and periodic reports to the regulatory authorities as required by applicable regulatory requirements.

11 STATISTICAL METHODS

11.1 Analysis Populations

The following analysis populations are defined for the study:

Efficacy Population – all patients who have received at least one dose of lucitanib and are confirmed as *FGFR1*-, 11q-amplified, or FGF non-amplified per the central laboratory.

Safety Population – all patients who have received at least one dose of lucitanib.

11.2 Statistical Methods

11.2.1 General Considerations

Patients randomized prior to implementation of Amendment #4 were stratified by FGF aberrancy (*FGFR1*- or 11q-amplified) and prior anti-angiogenic therapy (yes or no) status at baseline. Comparisons of the 15 mg and 10 mg dose groups may be stratified by these same factors. Patients that have amplification of both *FGFR1* and 11q are categorized as *FGFR1*-amplified for purposes of analysis. Since patients will no longer be randomized to the 15 mg dose group, the comparisons of the *FGFR1*-amplified, 11q-amplified, and FGF non-amplified subgroups will be made for the patients initially treated at 10 mg and for both dose groups.

Quantitative variables will be summarized using descriptive statistics (N, mean, standard deviation, median, minimum, and maximum) and/or frequency and percentages for medically relevant categories. Categorical variables will be presented using frequencies and percentages. Exact 95% confidence intervals may be presented for frequencies.

All data will be used to their maximum possible extent but without any imputations for missing data.

All statistical analyses will be conducted with the statistical analysis software (SAS[®]) system.

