5 STUDY DESIGN

5.1 Overall Study Design and Plan

This is a phase 2, open-label, multicenter study evaluating the efficacy and safety of lucitanib administered orally to patients with metastatic breast cancer. Patients with *FGFR1*- or 11q (FGF3, FGF4, Cyclin D1, or FGF19)-amplified metastatic breast cancer may be enrolled into one of two different cohorts (Cohort A: FGF-amplified or Cohort C: FGF non-amplified, both receiving 10 mg daily).

For patients with local *FGFR1* or 11q test results, a central laboratory will confirm the presence or absence of the *FGFR1* and/or 11q amplification. Central testing prior to enrollment for these patients is not required for study enrollment.

Patients with local *FGFR1* and 11q results for whom the central reading does not confirm the amplification status can continue the study at the discretion of the investigator if clinical benefit is observed. If there are a significant number of patients with discordant local and central testing results, additional patients may be enrolled.

For patients without a local *FGFR1* or 11q test result, tissue may be submitted for central testing under a prescreening process, and a positive central laboratory test result is required for screening and subsequent enrollment of these patients.

FGFR1-amplified and 11q-amplified patients will be enrolled* as follows:

- Cohort A (10 mg): approximately 80 patients

FGF non-amplified patients will be enrolled as follows:

- Cohort C (10 mg): up to 40 patients

The dose assigned to patients enrolled into Cohort C depends on the version of the amendment approved at the time of patient enrollment (Amendment #3: 15 mg; Amendment #4: 10 mg).

*Amendment #4 removes the 1:1 randomized treatment assignment (10 mg vs. 15 mg) and accrual of patients to Cohort B (15 mg). Up to 80 patients were expected enrolled into Cohort B under the previous versions of this protocol.

Up to 20 patients enrolled will participate in a PK sub-study to assess the comparative PK of the lucitanib tablet formulation taken at Day -7 with the lucitanib capsule formulation taken at Day 1.

Patients in Cohorts A or C will be enrolled in the PK sub study at participating sites, as follows:

- Participation in the PK sub study will be optional for patients participating in Cohort A
- Participation in the PK sub study will be required for patients participating in Cohort C until enrollment of the PK sub study is completed

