## **2** OVERALL STUDY DESIGN, OBJECTIVES, AND ENDPOINTS

## 2.1 Study Objectives and Endpoints

From the original protocol through amendment 5 of the protocol, there were three cohorts planned for which objectives and endpoints where defined. Cohort A was to have a starting dose of 10 mg daily of lucitanib; Cohort B was to have a starting dose of 15 mg daily of lucitanib; and Cohort C was added in amendment 2 and was to initially receive 15 mg daily of lucitanib. However, the major protocol amendment #4 discontinued the use of 15 mg as an initial starting dose thereby changing the initial starting dose for all subsequently enrolled patients in Cohort C to 10 mg of lucitanib as well as advising all investigators with patients receiving 15 mg lucitanib to dose reduce to 10 mg. Due to the significant changes to the protocol defined Cohorts and corresponding objectives and endpoints throughout the study, Table 1 below will only indicate those objectives and endpoints outlined in amendment #5 of the protocol.

Table 1. Primary, Secondary, and Exploratory Objectives and End	points
---	--------

Primary Objectives	Primary Endpoints
To estimate the anti-tumor efficacy of oral single-agent lucitanib as measured by investigator assessed PFS, when administered to patients with FGFR1 - or 11q-amplified breast cancer after failure of currently available standard therapies	Progression-free Survival (PFS) per RECIST Version 1.1 as determined by the investigator

Secondary Objectives	Secondary Endpoints	
To estimate the anti-tumor efficacy of oral single-agent lucitanib as measured by investigator assessed PFS, when administered to patients with FGFR1 - or 11q-amplified breast cancer after failure of currently available standard therapies	
 
ORR according to RECIST Version 1.1
 
DR and DCR according to RECIST Version 1.1
 
OS
 
	
To estimate patient-reported outcomes (PRO) following treatment with lucitanib	Change from baseline in PRO using the Functional Assessment of Cancer Therapy- Breast (FACT-B) questionnaire	
To evaluate the safety and tolerability of lucitanib	Treatment emergent AEs, laboratory abnormalities, physical examinations including vital signs and electrocardiogram (ECG) abnormalities	

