## **4** GENERAL ANALYSIS CONSIDERATIONS

Due to significant changes to the study design throughout the study, all summaries of data will be presented by initial study drug dose level (10 mg, 15 mg) regardless of a patient's enrollment into study cohorts A, B, and C. Initial dose groups will be referred to as treatment groups (10 mg, 15 mg). An overall column combining all patients from both treatment groups will be included in the data summaries, where applicable.

Quantitative variables will be summarized using descriptive statistics (N, mean, standard deviation, median, minimum, and maximum) and/or frequency and percentages for medically relevant categories. Categorical variables will be presented using frequencies and percentages. Exact 95% confidence intervals may be presented for frequencies.

All data will be used to their maximum possible extent but without any imputations for missing data.

All statistical analyses will be conducted with the statistical analysis software (SAS®) System, Version 9.3 or higher.

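### The 10 mg and 15 mg starting-dose columns pool randomised, non-randomised and non-amplified patients, so any comparison of them mixes dose with marker status and calendar period

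*Protocol*

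**What the plan says.** **Randomisation.** Under earlier protocol versions, amplified patients were randomised 1:1 to 10 mg (Cohort A) or 15 mg (Cohort B). Amendment #4 ended randomisation and accrual to Cohort B, and Cohort A continued at 10 mg (Protocol Synopsis, 3.7 and 5.1). Protocol 11.2.1 records that "Patients randomized prior to implementation of Amendment #4 were stratified by FGF aberrancy", with FGFR1 and 11q as the two levels, and by prior anti-angiogenic therapy.

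**Cohort C.** These non-amplified patients were never randomised. SAP 2.1: "Cohort C was added in amendment 2 and was to initially receive 15 mg daily of lucitanib". Protocol 5.1: "The dose assigned to patients enrolled into Cohort C depends on the version of the amendment approved at the time of patient enrollment", namely 15 mg under Amendment #3 and 10 mg under Amendment #4.

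**Comparison and display.** Protocol 11.2.1: "Comparisons of the 15 mg and 10 mg dose groups may be stratified by these same factors". SAP 4 says that all data summaries "will be presented by initial study drug dose level (10 mg, 15 mg) regardless of a patient's enrollment into study cohorts A, B, and C". SAP 12.1 then gives the Kaplan-Meier median by these treatment groups, and SAP 17 uses the same groups for safety.

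**Dose after Amendment #4.** SAP 2.1 describes the amendment as also "advising all investigators with patients receiving 15 mg lucitanib to dose reduce to 10 mg". Neither document says how many patients reduced, or when.

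**The concern.** The only protected evidence on dose in this study is the contrast between patients randomised to 10 mg and to 15 mg before Amendment #4. Neither document plans to show it. The specified display sets two pooled columns side by side, and a reader will compare them.

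The columns can differ for reasons other than starting dose. The share of non-amplified patients may differ, and Protocol 11.3 itself expects a smaller effect in Cohort C. Enrolment period also differs: nobody started at 15 mg under Amendment #4, while the 10 mg column goes on filling. Finally, patients in the 15 mg column may have spent part of their follow-up at 10 mg after the advice to reduce, so the columns describe the dose patients started on, not the dose received throughout.

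At stake is the reading of PFS, response and adverse events by dose, in a programme that moved to 10 mg because 15 mg was hard to sustain.

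**Working it through.** **1. The plan's own figures.** Protocol 11.3 and SAP 3 give precision for single groups only. Half-width of a 90% CI = 1.645 × √(p(1−p)/n), ignoring censoring.

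- n = 80, p = 0.50: 1.645 × √(0.25/80) = 9.2 points, lower limit 40.8%. The plan says under 10 points and above 40%; this reproduces.
- n = 40, p = 0.25: 1.645 × √(0.1875/40) = 11.3 points, upper limit 36.3%. The plan says under 15 points and below 40%; this reproduces.

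No figure is given for 10 mg against 15 mg, so these results say nothing about the dose contrast.

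**2. Who is in each column under SAP 4.**

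| Column | Randomised | Not randomised |
|---|---|---|
| 10 mg | Cohort A before Amendment #4 | Cohort A after Amendment #4; Cohort C started at 10 mg |
| 15 mg | Cohort B | any Cohort C started at 15 mg |

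**3. Can the named strata repair it?** The FGF factor has the levels FGFR1 and 11q. A non-amplified patient belongs to neither. The second factor is prior anti-angiogenic therapy. Neither factor separates enrolment before from after Amendment #4. A stratified comparison of the pooled columns would therefore leave both sources of imbalance in place.

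**4. How large could marker mix alone be?** Assumptions: no dose effect; 6-month PFS 50% in amplified and 25% in non-amplified patients; Cohort A = 80; Cohort C = 40 over both doses (80 + 80 + 40 = 200, the stated maximum). Let k be the number of Cohort C patients who started at 15 mg and B the size of Cohort B.

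- 10 mg rate = (80 × 0.50 + (40 − k) × 0.25) / (120 − k)
- 15 mg rate = (B × 0.50 + k × 0.25) / (B + k)

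| k | B | 10 mg | 15 mg | 15 minus 10 |
|---|---|---|---|---|
| 0 | any | 41.7% | 50.0% | +8.3 points |
| 20 | 80 | 45.0% | 45.0% | 0 |
| 40 | 80 | 50.0% | 41.7% | −8.3 points |
| 40 | 20 | 50.0% | 33.3% | −16.7 points |

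With 40% in place of 50% for amplified patients, the range is +5 to −10 points. The rates of 50% and 25% are borrowed from the confidence-interval illustrations in Protocol 11.3 and are not forecasts. The values of k and B are not in the documents. Calendar period and the advised reduction are not included.

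**5. Precision of the randomised contrast.** For a difference between two arms of n each with rates near 50%, the 90% half-width = 1.645 × √(0.5/n), without censoring.

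- n = 22: 1.645 × √(0.5/22) = 24.8 points
- n = 40: 1.645 × √(0.5/40) = 18.4 points

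The number randomised is not stated; 22 to 40 per arm is an assumption.

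**The case against.** The strongest reply is that no dose contrast is planned as an inference. The primary objective is to estimate PFS in amplified patients. No objective compares doses, and there is no test, hazard ratio, alpha or power for 10 mg against 15 mg. Protocol 11.2.1 says only that comparisons may be stratified, and the SAP gives columns and a Kaplan-Meier median by group. That stands, and it limits the point to interpretation.

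The sentence in Protocol 11.2.1 follows one about patients randomised before Amendment #4 and could be read as referring to them. That reading is possible but not stated, and SAP 4 pools in plain terms.

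The protocol also offers partial handling. Section 11.2.1 foresees comparisons of FGFR1-amplified, 11q-amplified and non-amplified patients, and 11.2.4 allows results by cohort. SAP 12 carries neither forward, and FGF status appears in the SAP only as a baseline characteristic (8.2). The adverse-event tables that SAP 17.1 lists by cohort would still mix randomised and later Cohort A patients.

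A reader might infer that the columns are mislabelled because 15 mg patients moved to 10 mg. The documents do not support that. SAP 4 calls them initial dose groups, which is correct for every patient, and SAP 9 reports mean daily dose. Investigators were advised to reduce the dose; how many patients did so is unknown.

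Last, the randomised contrast is imprecise: its interval may be wider than most of the bias illustrated. That is a real cost. It does not make the pooled difference a valid estimate of a dose effect.

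**Conclusion.** The point holds as a gap in interpretation and specification. The pooled starting-dose columns are not a fair dose comparison, the strata named for adjustment cannot make them one, and the randomised comparison the study already contains is not prespecified.

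The size and direction of any distortion cannot be computed from the documents. Under the stated assumptions, marker mix alone gives anything from +8.3 to −16.7 points for 15 mg minus 10 mg.

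Three stronger readings should be resisted:

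- That 10 mg will look falsely worse by about 8 points. This requires that no Cohort C patient started at 15 mg, yet the documents assign that dose to Cohort C before Amendment #4.
- That only a small part of the 10 mg column is randomised. The 43 patients of this study in the safety data of 21 May 2015 are not broken down by cohort. The Synopsis puts Cohort B at up to 80, so with 1:1 allocation randomised Cohort A could approach 80, or 80/120 = 67% of a column of 120.
- That a primary test is invalidated. The dose comparison is optional and no primary test depends on it.

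**What to change.** In Protocol 11.2.1 and SAP 4, 12 and 17:

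- Confine any 10 mg versus 15 mg comparison to patients randomised before Amendment #4, analysed by assigned dose with the two randomisation strata (FGFR1 or 11q; prior anti-angiogenic therapy).
- State that this compares starting doses, since patients on 15 mg may have reduced to 10 mg.
- State that the pooled starting-dose columns are descriptive and are not a dose comparison.
- If follow-up at the starting dose is of interest, add an analysis cut at each patient's recorded date of reduction from 15 mg, as a sensitivity analysis only. Such a cut risks informative censoring, and the documents give no common date for the advice that could serve instead.

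The cost is a change of wording and one added set of tables from data already collected, with no change to conduct. The downside is the wide interval for the dose contrast shown above (about ±18 to ±25 points at 22 to 40 patients per arm), which should be reported alongside the estimate.
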